## Introduction

This section outlines the key statistical considerations for the human studies aspects of the grant proposal. For each of our specific aims we provide outlines for the analysis plans, along with corresponding rationale for choice of study design with associated sample sizes.

## Study Design

The main study design is that of randomized clinical trial assessing the effects of 3 months of resistance exercise (RE) training relative to a sedentary control (SC) condition in insulin resistant (IR) study volunteers. A total of 48 IR individuals meeting inclusion/exclusion criteria as outlined in the application will be enrolled. Baseline measures will be obtained after which they will be randomized in a 2:1 ratio to RE (n=32) versus SC (n=16). After 3 months, baseline measures will be repeated, with the expectation of improvements in measures in the RE-trained arm.

We will additionally recruit a group of 16 insulin sensitive (IS) individuals, in whom the same measures will be obtained, at baseline only.

## Rationale for Randomized Trial Design

Initially it may seem that a single arm study whereby all individuals receive RE training would be sufficient to answer the questions of interest; however, by including a sedentary control group, if measures increase in the RE-trained group, but not in the SC group, we will have more confidence that the training is causative of the changes. It is possible that some measures may change over time, for example consequent to seasonal effects.

### Rationale for Randomization Ratio

In order to be as efficient in our design, we propose a 2:1 randomization ratio; we devote relatively more resources to the RE training arm, as the individuals receiving RE training are of primary interest. In addition to learning whether our measures of interest change over time in this group (and relative to the sedentary control group), we will seek to explore the extent to which changes in some measures relate to others and this will benefit from as large a sample size as possible; in contrast there is relatively little to be learned from the control group other than to check that there are no changes of consequence over the 3 month study time period in this group.

## Rationale for Insulin Sensitive Comparator Group

The premise underlying the proposal is that insulin resistance can to some extent be ameliorated by RE training. It is thus important to demonstrate that (i) key measures of interest actually do differ in IR people compared to IS people, and (ii) that any changes in these measures with RE training do indeed differ in the expected direction – closer to those of IR people. Although we do not dramatic changes with only 3 months of training, it will be of additional benefit to be able to quantify, even if informally, the proportional

extent to which improvements can be made in measures relative to the group of IS people that we recruit.

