### **Statistical Analysis**

*Aim 1 - Change in muscle strength*

*Endpoint:*  $\Delta(1RM \text{ normalized to lean mass}) = [1RM \text{ at 3 months} / \text{DEXA lean mass at 3 months}] - [1RM \text{ at baseline} / \text{DEXA lean mass at baseline}]$ .

*Primary analysis:* Two-sample t-test (RE vs SC) on  $\Delta$  normalized 1RM.

*Aim 2 - Change in insulin sensitivity*

*Endpoint:*  $\Delta(\text{Insulin AUC})$  where AUC ( $\mu\text{IU} \cdot \text{min}/\text{mL}$ ) is computed from time points -20, 0, 10, 20, 30, 60, 90, 150, 240 min using the trapezoidal rule.

*Primary analysis:* Two-sample t-test (RE vs SC) on  $\Delta\text{AUC}$ .

*Aim 3 - Change in lean mass*

*Endpoint:*  $\Delta$  total lean mass (kg) by DEXA.

*Primary analysis:* Two-sample t-test (RE vs SC) on  $\Delta$  lean mass.

*Aim 4 - Change in body fat percentage*

*Endpoint:*  $\Delta$  total body fat percentage by DEXA.

*Primary analysis:* Two-sample t-test (RE vs SC) on  $\Delta$  fat %.

Aims 1-4 data will be presented as mean  $\Delta \pm \text{SD}$  in RE vs SC and p-value.

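### Does the plan need a prespecified analysis for the 16 insulin-sensitive participants?

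*Combined protocol and SAP*

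**What the plan says.** Study Design: "We will additionally recruit a group of 16 insulin sensitive (IS) individuals, in whom the same measures will be obtained, at baseline only". The 48 IR participants are randomised 2:1, 32 to RE and 16 to SC.

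Rationale for Insulin Sensitive Comparator Group: the IS group is there to show that "key measures of interest actually do differ in IR people compared to IS people" and that changes with training go the expected way, which is described as "closer to those of IR people". As a further benefit, the authors would like to "quantify, even if informally, the proportional" extent of improvement relative to the IS group.

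Statistical Analysis: four two-sample t-tests, all RE versus SC on a 3-month change. The reporting line, which begins "Aims 1-4 data will be presented as mean", covers RE and SC only and gives SD and p-value. The IS group does not appear.

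Two other sections bear on how a proportion might be formed. Rationale for Randomization Ratio speaks of "learning whether our measures of interest change over time in this group (and relative to the sedentary control group". Rationale for Randomized Trial Design gives the reason for a control arm: "It is possible that some measures may change over time, for example consequent to seasonal effects".

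**The concern.** Sixteen of the 64 people studied (48 + 16) are recruited for a comparison that the rationale calls important, and the only analysis section supplied does not describe it. The analysis cannot be copied from the four aims either, because each endpoint is a change and IS participants are measured once.

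The proportional comparison looks looser still. The change could be taken within RE or relative to SC, and the two give different percentages from the same data. If a measure drifted over three months in both arms, the within-RE version would count the drift as progress towards the IS group. A bare percentage would also suggest more precision than these sample sizes support. The only phrase describing the expected direction names the wrong group.

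At stake is what gets reported about the IS group: measures, numerator or direction could be chosen after the data are seen.

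**Working it through.** The plan gives no SD, effect size, power or formula for the IS group, so it has no figure to reproduce. From the plan: IR 48 (RE 32, SC 16) and IS 16. Assumed: equal baseline SD of 1, no dropout, two-sided 5%, IS-IR gap of 1.0 to 2.0 SD, pre-post correlation r of 0.5 to 0.9, observed closure of 30%.

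**1. Baseline IR versus IS.** SE = sqrt(1/48 + 1/16) = 0.289 SD. Half-width of the 95% CI = t(0.975, 62 df) × SE = 2.00 × 0.289 = 0.58 SD. A t-test has 80% power at a difference of 0.82 SD. The comparison is feasible, and its inputs follow from the plan: each of the four endpoints is built from a baseline value, and the IS group has the same measures at baseline.

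**2. Precision of a proportion.** Take the RE minus SC difference in change over the baseline gap. SD of change = sqrt(2(1 − r)); SE of the numerator = SD of change × sqrt(1/32 + 1/16) = SD of change × 0.306; SE of the gap = 0.289. Numerator and gap are uncorrelated, because the shared baseline term cancels between arms. Fieller limits for a 30% closure:

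| Gap (SD) | r | SD of change | 95% limits |
|---|---|---|---|
| 1.0 | 0.5 | 1.000 | -33% to 121% |
| 1.5 | 0.7 | 0.775 | -1% to 71% |
| 2.0 | 0.9 | 0.447 | 16% to 49% |

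**3. Choice of numerator.** The two versions differ by (SC mean change)/gap. If SC truly does not change, the SD of that difference is sqrt(2(1 − r))/4/gap: 25.0 points (1.0, 0.5), 12.9 (1.5, 0.7) and 5.6 (2.0, 0.9). An assumed drift of 0.2 SD common to both arms adds 0.2/2.0 = 10% to 0.2/1.0 = 20% to the within-RE version and nothing to the other. A one-sample test in SC would detect that drift 12%, 16% or 39% of the time at r = 0.5, 0.7 or 0.9.

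**4. Would a fixed rule help?** The obvious rule is the RE minus SC ratio with a Fieller interval for all four endpoints. That interval is bounded only if the gap differs significantly from zero, so the observed gap must exceed 1.96 × 0.289 = 0.57 SD. With r = 0.7 and 30% closure:

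- Gap 0.6: numerator 0.18, variance 0.6 × 0.09375 = 0.05625. Limits = (0.18 × 0.6 ± sqrt(0.108² + 0.0399 × 0.1837))/0.0399 = -75% to 616%. Here 0.0399 = 0.36 − 3.84 × 0.0833 and 0.1837 = 3.84 × 0.05625 − 0.0324.
- Gap 0.5: no finite limits; the set is the whole line.

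With a true gap of 0.5 SD, the observed gap would be non-significant about 59% of the time (0.5/0.289 = 1.73; 1.96 − 1.73 = 0.23; normal probability 0.59, the other tail being negligible).

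**5. The slip.** RE participants are themselves IR, so training cannot be expected to move them towards IR values. The sentence makes sense only with IS, and no test, endpoint or sample size uses it.

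**The case for a change.** The best case for acting is that a stated purpose of the study deserves a stated analysis, that the Introduction presents this document as the place for analysis outlines, and that a corrected word with two or three sentences would cost almost nothing. The arithmetic in steps 1 to 3 is sound under its assumptions, and a within-RE percentage could indeed mislead.

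Part of this stands: the IS comparison is not written into Statistical Analysis, and the wording slip is real. The rest carries less weight.

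- The Introduction promises outlines for the specific aims. Neither IS comparison is one of Aims 1-4.
- No section proposes the within-RE percentage. The sentence that yields two possible numerators is about the allocation ratio, while the argument for having a control arm already points to a control-referenced change.
- The expected direction is not wholly absent: for insulin AUC it follows from how the two groups are defined.
- A prescribed ratio brings its own difficulties. It can have no finite interval, and it is hard to interpret where training and the gap point in opposite directions, as they would for lean mass if IR participants had more of it.
- The IS group is not randomised, and allocation balances age and sex only between the two trial arms. A raw IR-IS difference needs that caution whether or not a formula is written down.
- The key measures may be set out in the grant application, which is not among the documents.

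**Conclusion.** No change is called for. The missing IR-IS analysis is a gap in detail that analysts would fill sensibly: the plan says the groups will be compared, both have the same baseline measures, and the natural report is a baseline difference with an interval of about ±0.58 SD, read with age and sex in mind. That half-width assumes equal SDs and no dropout.

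The proportion is an informal extra. Its imprecision (-1% to 71% in the middle case, -33% to 121% at the widest) is a reason to read it lightly, and every such figure rests on assumed gaps and correlations. No stated method gives a wrong answer, and a mandatory ratio for all endpoints would break down at observed gaps below about 0.57 SD. The IR-for-IS wording is clerical. The design, the sample sizes and the four RE versus SC tests do not depend on any of these points.

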### **Procedures for Randomization and Blinding**

We will create a dynamic randomization allocation algorithm structured to minimize imbalance with respect to key baseline variables including age and sex. This will be implemented with a web interface in a SAS application with restrictions so that access is granted only on a need-to-know basis. The study statistician will be able to monitor assignments globally to ensure the algorithm is working appropriately and the study coordinator (with a back-up) will be able to log in to access randomization assignment for each individual study participant on a prospective basis. All members of the research team involved in obtaining any of the measures will be blinded (to the extent possible) to the assignment of individuals to study arms. Those study team members involved in training will, of course, not be blinded. Randomization assignment data will be merged with the rest of the study data according to study identification numbers only as needed for analysis, otherwise they will remain separate until the studies are completed.

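### Allocation is minimised on age and sex, but the Aim 1-4 t-tests use neither; if both predict change similarly in the two arms, the tests are conservative and adjustment recovers power

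*Combined protocol and SAP*

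**What the plan says.** Procedures for Randomization and Blinding plans a "dynamic randomization allocation algorithm structured to minimize imbalance with respect to key baseline variables including age and sex". The word including leaves the list of factors open, and the section gives no weights, age categories or random element.

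Statistical Analysis gives the same kind of primary analysis for each of the four aims: "Two-sample t-test (RE vs SC) on" the change in normalised 1RM, insulin AUC, lean mass or fat percentage. On reporting it says "Aims 1-4 data will be presented as mean" change with SD in each arm and a p-value. No covariate, stratified or re-randomisation analysis appears for any aim, and no adjusted estimate or confidence interval is planned.

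Study Design sets the size: "A total of 48 IR individuals meeting inclusion/exclusion criteria as outlined in the application will be enrolled", split 2:1 into 32 RE and 16 SC. Rationale for Randomization Ratio describes the controls as there mainly to "check that there are no changes of consequence over the 3 month study time period in this group".

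**The concern.** Balancing the arms on a factor that predicts the outcome removes part of the chance variation in the difference between arms. An unadjusted t-test estimates its standard error from the whole within-arm variance, including the part that balancing has removed from the comparison. The standard error is then too large and the test rejects less often than its nominal level. A model that includes the balancing factors restores the correct standard error.

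With 48 randomised participants and only 16 controls, a test below its nominal level may miss an effect that the same data could have shown. Age and sex will already be recorded for every participant because the algorithm needs them.

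The argument depends on age and sex predicting change similarly in both arms. If they predict nothing, there is no problem. If they predict change only in RE, the mechanism largely disappears.

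**Working it through.** **Inputs from the documents.** N = 48; 48 x 2/3 = 32 RE and 48 x 1/3 = 16 SC, as stated. Allocation is dynamic on age and sex, and the tests are unadjusted. The total of 48 cannot be reproduced, because no alpha, power, effect size, SD or dropout is given.

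**Assumptions.** Two-sided 5% alpha; effect 0.8 SD; share of change-score variance explained by age and sex (R2) from 0 to 0.30; no dropout; sex 50/50; age in quartiles for allocation; biased coin 0.85.

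**Analytic check (equal prediction, perfect balance, total variance 1).**
- Expected t-test SE = sqrt(1/32 + 1/16) = sqrt(0.09375) = 0.306.
- True SD of the difference = sqrt(1 - R2) x 0.306, which is 0.290 / 0.274 / 0.256 at R2 0.10 / 0.20 / 0.30.
- Large-sample type I error = 2 x P(Z > 1.96/sqrt(1 - R2)) = 3.9% / 2.8% / 1.9%.

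Minimisation does not balance perfectly, so the real effect is smaller and needs simulation.

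**Simulation (40,000 trials per cell; Monte Carlo error about 0.2 points on power, 0.1 on type I error).** The outcome is y = sqrt(R2) x score + sqrt(1 - R2) x e in both arms, where the score weights standardised sex and age equally and has unit variance. The pooled t-test (46 df) is compared with a linear model on arm, sex and age (44 df).

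| R2 | t-test SE overstated by | t-test type I error | Power, t-test | Power, adjusted | Gain (points) |
|---|---|---|---|---|---|
| 0 | 0% | 5.0% | 72.9% | 72.3% | -0.6 |
| 0.05 | 2% | 4.5% | 73.2% | 74.4% | +1.2 |
| 0.10 | 4% | 4.2% | 73.2% | 76.4% | +3.2 |
| 0.20 | 9% | 3.3% | 74.6% | 81.4% | +6.8 |
| 0.30 | 14% | 2.6% | 75.4% | 86.1% | +10.7 |

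The SE column can be checked by hand. Mean arm sizes were 31.6 and 16.4, so the t-test SE is about sqrt(1/31.6 + 1/16.4) = 0.304. Dividing by the simulated true SDs of 0.292 / 0.280 / 0.267 at R2 0.10 / 0.20 / 0.30 gives 1.04 / 1.09 / 1.14.

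The adjusted model's type I error is 4.8-5.1% throughout this case. Coin settings of 0.75 and 1.0 leave the gain at 3 / 7 / 11 points for R2 0.10 / 0.20 / 0.30.

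**Is minimisation the cause?** A separately programmed simulation (6,000 trials per cell, three age categories, effect 0.88 SD) gave t-test type I error of 4.5% / 3.6% / 2.6% at R2 0.10 / 0.20 / 0.30. Under plain 32/16 randomisation it stayed at 5.0-5.5%. Gains from adjusting were about 3, 5-6 and 9 points.

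**Where the gain comes from.** Adjustment lowers the true SD only from 0.292 / 0.280 / 0.267 to 0.290 / 0.274 / 0.256, a fall of 0.7% / 2.1% / 4.1%. Most of the gain is a correct standard error rather than a sharper estimate.

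**Unequal prediction (R2 0.10 / 0.20 / 0.30).**
- *RE only, equal total variance:* t-test type I error 4.9% / 4.8% / 4.8%; true SD 0.304 / 0.302 / 0.300 unadjusted against 0.305 / 0.304 / 0.302 adjusted. There is no gain, and the model-based type I error rises to about 5.4% / 5.9% / 6.4%.
- *RE only, equal residual variance:* the pooled t-test is conservative (4.4% / 4.0% / 3.4%), mainly because it pools unequal variances at 2:1; Welch gives 4.6-4.7%. With both tests set to a true 5% level, power is 77.0% / 80.0% / 83.3% unadjusted against 76.5% / 79.9% / 83.0% adjusted.
- *SC slope half the RE slope:* the true SD improves by at most about 1.5%. With equal total variance, the model-based type I error is 5.3% / 5.5% / 6.1%.
- *HC3 standard errors* hold type I error at 4.1-4.3% in the unequal-prediction, equal-total-variance cases.

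**The case against.** The strongest reply is that the plan contains no error. The t-test is unbiased and does not exceed its nominal level, and no passage promises an adjusted analysis. That stands, and it is why the point is only a suggestion.

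The second objection is that the condition may fail. A control group expected to show little change makes prediction mainly in RE plausible. That expectation concerns the mean rather than who changes more, so it does not settle the question, but no gain is claimed in that case. The R2 is also unknown and may be low because all four endpoints are change scores; at 0.05 or less the gain is about one point or none.

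Third, the remedy has a cost. Under unequal prediction with equal total variance, the model-based SE turns a calibrated or conservative test into a slightly anti-conservative one. HC3 corrects that but gives back power:
- Equal prediction: HC3 power is 73.2% against 73.1% for the t-test at R2 0.10, so no gain. At R2 0.20 and 0.30 it keeps one (78.0% and 83.5% against 74.1% and 75.0%).
- Half slope in SC, equal total variance, R2 0.10 / 0.20 / 0.30: HC3 gives 70.6% / 72.4% / 74.6% against 72.8% / 72.9% / 73.4%. With the model-based SE and t-test both set to a true 5% level, the gain is under one point.
- RE-only prediction: HC3 power is about 69% against about 73%.

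These figures stand and confine the benefit to roughly similar prediction in the two arms. They do not remove the mismatch between allocation and analysis, or the need to name the balancing factors.

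Last, the Introduction calls these plans outlines, so fuller detail may exist elsewhere. Even so, Statistical Analysis states each primary analysis in full and without covariates.

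**Conclusion.** The point holds as a modest efficiency suggestion, with medium confidence. Allocation uses age and sex and the analysis ignores them. If the two factors predict change similarly in both arms, the planned tests run at about 4.2% / 3.3% / 2.6% instead of 5% for R2 of 0.10 / 0.20 / 0.30, and adjustment recovers about 3 / 7 / 11 power points. At R2 of 0.05 the gain is about 1 point, and at zero there is a loss of about half a point.

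All sizes rest on assumed R2, effect, alpha and algorithm settings. Under RE-only prediction no gain is claimed, and under a half slope in SC any real precision gain is very small. Keeping the planned t-test would be defensible.

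**What to change.** Consider these changes to Statistical Analysis, made before any outcome is seen:

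1. List every variable the allocation algorithm uses, not only age and sex. This is useful whatever the R2.
2. For each of Aims 1-4, pre-specify a linear model of the change score on arm plus the balancing factors: age as continuous, sex, and any other listed variable. Report the adjusted RE-SC difference with its 95% confidence interval and p-value, beside the planned mean and SD by arm.
3. Pre-specify two sensitivity analyses: the same model with HC3 standard errors, and the planned unadjusted t-test. Both are needed because the model-based SE can be too small when residual variance is larger in the smaller SC arm. State that the adjusted model is the analysis on which each aim is judged and that these two only support its interpretation.

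**Cost.** SAP wording only; age and sex are already collected. Adjusting for both takes the residual degrees of freedom from 46 to 44, with more used if the algorithm has further factors. It loses about 0.5 power points if the factors are not prognostic. The risk is a model-based type I error of up to about 6.4% in the unequal-prediction cases examined, which the HC3 analysis is there to reveal.

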### **Statistical Analysis**

*Aim 1 - Change in muscle strength*

*Endpoint:*  $\Delta(1RM \text{ normalized to lean mass}) = [1RM \text{ at 3 months} / \text{DEXA lean mass at 3 months}] - [1RM \text{ at baseline} / \text{DEXA lean mass at baseline}]$ .

*Primary analysis:* Two-sample t-test (RE vs SC) on  $\Delta$  normalized 1RM.

*Aim 2 - Change in insulin sensitivity*

*Endpoint:*  $\Delta(\text{Insulin AUC})$  where AUC ( $\mu\text{IU} \cdot \text{min}/\text{mL}$ ) is computed from time points -20, 0, 10, 20, 30, 60, 90, 150, 240 min using the trapezoidal rule.

*Primary analysis:* Two-sample t-test (RE vs SC) on  $\Delta\text{AUC}$ .

*Aim 3 - Change in lean mass*

*Endpoint:*  $\Delta$  total lean mass (kg) by DEXA.

*Primary analysis:* Two-sample t-test (RE vs SC) on  $\Delta$  lean mass.

*Aim 4 - Change in body fat percentage*

*Endpoint:*  $\Delta$  total body fat percentage by DEXA.

*Primary analysis:* Two-sample t-test (RE vs SC) on  $\Delta$  fat %.

Aims 1-4 data will be presented as mean  $\Delta \pm \text{SD}$  in RE vs SC and p-value.
